8.6 Follow-up of subjects withdrawn from treatment

Subjects withdrawn from the study will not be followed up unless it seems necessary in case of any urgent medical reason.

8.1 Premature termination of the study

There are no expected reasons for premature termination of the study. However, in the event of urgent medical issues arising during the study (for example SAEs that result in death or are life threatening) the investigator (if necessary, together with the medical committee) can decide to halt the study to check whether it is safe to proceed or if termination is preferred.

9. SAFETY REPORTING

9.1 Temporary halt for reasons of subject safety

In accordance to section 10, subsection 4, of the WMO, the sponsor will suspend the study if there is sufficient ground that continuation of the study will jeopardise subject health or safety. The sponsor will notify the accredited METC without undue delay of a temporary halt including the reason for such an action. The study will be suspended pending a further positive decision by the accredited METC. The investigator will take care that all subjects are kept informed.

9.2 AEs, SAEs and SUSARs

9.2.1 Adverse events (AEs)

Adverse events are defined as any undesirable experience occurring to a subject during the study, whether or not considered related to transcutaneous auricular vagal nerve stimulation or the nausea induction by intragastric lipid infusion. All adverse events reported spontaneously by the subject or observed by the investigator, or his staff will be recorded. Subjects are promptly asked to report any changes in their health in the 24 hours following the test day via phone or email to the coordinating investigator. These adverse events will then be recorded in Castor.

9.2.2 Serious adverse events (SAEs)

A serious adverse event is any adverse event that led to any of the following:

- Death,
- Serious deterioration in the health of the subject, that resulted in any of the following:
 - o Life-threatening illness or injury,
 - o Permanent impairment of a body structure or a body function,
 - o Hospitalisation or prolongation of patient hospitalisation,
 - o Medical or surgical intervention to prevent life-threatening illness or injury or permanent impairment to a body structure or a body function,
 - o Chronic disease,
- Foetal distress, foetal death or a congenital physical or mental impairment or birth defect.

An elective hospital admission will not be considered as a serious adverse event.

The investigator will report all SAEs to the sponsor without undue delay after obtaining knowledge of the events. The sponsor will report the SAEs through the web portal *Research Portal* to the review committee that approved the protocol, within 7 days of first knowledge for SAEs that result in death or are life threatening followed by a period of maximum of 8 days to complete the initial preliminary report. All other SAEs will be reported within a period of maximum 15 days after the sponsor has first knowledge of the serious adverse events.

9.2.3 Suspected unexpected serious adverse reactions (SUSARs)

Not applicable.

9.3 Annual safety report

Not applicable.

9.4 Follow-up of adverse events

All AEs will be followed until they have abated, or until a stable situation has been reached. Depending on the event, follow up may require additional tests or medical procedures as indicated, and/or referral to the general physician or a medical specialist. SAEs need to be reported till end of study within the Netherlands, as defined in the protocol.

9.5 [Data Safety Monitoring Board (DSMB) / Safety Committee]

Not applicable.

10. STATISTICAL ANALYSIS

Demographic data and patient-reported data will be collected and saved in Castor EDC. Database cleaning will be carried out by internal consistency checks and identification of database entries outside expected ranges by the study coordinator and the local research nurses. Primary and secondary outcomes will be analyzed based on a modified intention-to-treat (ITT) approach. SPSS, R, Python, and Excel will be used to perform the statistical analysis.

Subject characteristics will be presented and analysed using descriptive statistics. Continuous parameters will be presented as means and standard deviations, and assessed between the two groups (taVNS vs. sham) with a two-sample unpaired t-test (for normally distributed data) or a nonparametric Mann-Whitney U test (for non-normally distributed data). Categorical variables will be represented as frequencies and analyzed using a Chi-square test or a Fisher's exact test. A p-value < 0.05 will be considered statistically significant. No missing data are expected; however, if present, missing data will be handled using appropriate statistical methods.

The modified intention-to-treat population will be defined as all randomized participants who successfully complete the nausea induction procedure and in whom the intervention (taVNS or placebo) is initiated. All primary and secondary outcome analyses will be conducted based on this analysis set.

10.1 Primary study parameter(s)

To assess the effect of taVNS on nausea severity, Visual Analogue Scale (VAS) scores will be compared at various timepoints following nausea induction between the taVNS and sham stimulation groups. A linear mixed-effects model (LMM) will be utilized to evaluate both intergroup differences and within-group changes in VAS scores over time. LMM offers flexibility by adjusting for baseline nausea severity (if needed), handling missing data, and accounting for individual variability through random effects. LMM uses all available data points for each individual in likelihood estimation, rather than excluding participants with missing data. If LMM assumptions are violated, a nonparametric alternative may be considered. Potential confounding factors will be included as covariates in the LMM to adjust for their effects. Differences in VAS scores will be reported along with their corresponding 95% confidence intervals (CIs) and two-sided p-values, using a significance level (type I error rate) of 0.05.

10.2 Secondary study parameter(s)

The effects of taVNS compared to sham stimulation on other gastrointestinal complaints, the desire to eat, plasma levels of ghrelin and motilin, and salivary cortisol levels following nausea induction, will be analyzed using a linear mixed-effects model, consistent with the approach used for the primary outcome.

To assess the relationship between the nausea response and scores on the questionnaires measuring affective symptoms and personality traits (GAD-7, PHQ-9, and BFI), LMM with questionnaire scores as covariates will be used.

To evaluate the effect of taVNS vs. sham on autonomic parameters, including heart rate variability and skin conductance, a linear mixed-effects model will be employed. This model allows for the evaluation of the impact of taVNS on each autonomic parameter while accounting for within-subject correlations and missing data.

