2.2 Secondary Objectives

1. To assess the effect of taVNS on other gastrointestinal symptoms, such as bloating, abdominal pain, and fullness, following intragastric lipid infusion, compared to sham stimulation.

Hypothesis: We hypothesize that taVNS will lead to a significant reduction in other gastrointestinal symptoms, such as bloating, abdominal pain, and fullness, compared to sham stimulation, as measured by a 0-100 Visual Analogue Scale (VAS) score at regular time intervals.

2. To explore the effects of taVNS on the desire to eat following nausea induction, compared to the sham stimulation group.

Hypothesis: We hypothesize that taVNS will lead to an earlier increase in the desire to eat following nausea induction compared to sham stimulation, as measured by a 0-100 Visual Analogue Scale (VAS) at regular time intervals.

3. To investigate the effect of taVNS on plasma levels of ghrelin and motilin following nausea induction.

Hypothesis: We hypothesize that nausea induction will result in a reduction in plasma levels of ghrelin and motilin, and that this reduction will be counteracted by taVNS.

4. To investigate the effects of taVNS on salivary cortisol levels following nausea induction.

Hypothesis: We hypothesize that nausea induction will result in an increase in salivary cortisol levels, and that this increase will be attenuated by taVNS.

5. To evaluate how affective symptoms and personality traits, utilizing the GAD-7, PHQ-9, and BFI, influence the nausea response.

Hypothesis: We hypothesize that affective symptoms, such as anxiety, and personality traits will modify the nausea response.

6. To evaluate the effect of taVNS on parameters related to autonomic outflow, using a Fitbit smartwatch for heart rate variability (HRV), and a Shimmer3 GSR sensor for HRV and skin conductance.

Hypothesis: We hypothesize that treatment with taVNS will lead to significant changes in the autonomic outflow reflective of an increase in parasympathetic activity.

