5.2 Use of co-intervention

5.2.1 Intragastric lipid infusion

As a co-intervention, an intragastric infusion of a 50% fat emulsion in water will be administered to induce nausea. A 10-F gauge single-lumen polyurethane nasogastric tube (Nutricair Enteral-Enfit, Charrière 10) will be manually inserted by the coordinating investigator, positioning the catheter in the stomach and connecting it to a nutrition enteral delivery pump (Applix Smart pomp). A 20/60ml Nutricair Enteral-Enfit syringe will be used to administer the fat emulsion through the feeding tube. Standard clinical protocols for nasogastric tube placement will be followed, including a pH measurement to verify the tube's position, ensuring participant's safety and comfort.

The fat emulsion (Calogen, NUTRICIA, Netherlands) used is comparable to that employed in previous research on intragastric nausea induction (1). It is a medical nutritional product typically used to address an 'energy deficit' in patients who are unable to meet their recommended energy intake through regular food and/or oral nutritional supplements. The emulsion is suitable for enteral use and can be administered via a nasogastric tube (31). See D6.1_SPC_Calogen_Versie1.0_dd 16-10-2024 & D6.2_Calogen_Voedingstabel_Versie1.0_dd 15-10-2024 for additional information.

The fat emulsion consists of 50% long-chain triglyceride and 50% water (osmolality: 0 mOsm/L, Calogen, NUTRICIA, Netherlands). Previous research has shown that long-chain triglycerides elicit a stronger nausea response than medium-chain triglycerides, which is why long-chain triglycerides were selected as the primary component (1). The infusion rate will be set at 5 ml/min (22.5 kcal/min) and will continue until the participant experiences nausea, indicated by a VAS score of 50/100 (1). Based on previous studies, it is expected that approximately 258 + 32 ml of the fat emulsion is required to induce nausea through gastric relaxation, with the process taking approximately 52 ± 6 minutes (1). If the nausea score does not reach the VAS of 50/100 after 1.5 hours of infusion, the infusion will be discontinued, and the test day will be terminated. In this case, the participant will be considered a drop-out due to non-response to the nausea-inducing stimulus.

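### Objective 5: the fixed analysis set and titration to VAS 50 leave the planned model describing mainly nausea after induction, so it cannot show whether anxiety, mood or personality relate to susceptibility

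*Protocol*

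**What the plan says.** Protocol section 2.2, objective 5: "To evaluate how affective symptoms and personality traits, utilizing the GAD-7, PHQ-9, and BFI, influence the nausea response". Its hypothesis is that "affective symptoms, such as anxiety, and personality traits will modify the nausea response". Section 8.1.2 lists the matching endpoint and does not define nausea response.

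Section 10.2 gives the method: "LMM with questionnaire scores as covariates will be used". It names neither the outcome variable nor the time window. The primary model in section 10.1 uses VAS scores after induction.

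Section 10 defines the modified ITT set as "all randomized participants who successfully complete the nausea induction procedure and in whom the intervention (taVNS or placebo) is initiated", and adds: "All primary and secondary outcome analyses will be conducted based on this analysis set".

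Section 5.2.1 runs the infusion at 5 ml/min until VAS 50/100, with a limit of 1.5 hours. For anyone below 50 at that point the test day ends, and "the participant will be considered a drop-out due to non-response to the nausea-inducing stimulus". Section 8.5 excludes dropouts from analyses.

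Section 8.3.2 has VAS rated every 5 minutes during the infusion. Section 8.3.4 counts 14 nausea questionnaires: one at baseline, one when the infusion stops, six during stimulation and six afterwards. None falls within the infusion.

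**The concern.** Titration sets the end-of-induction score to roughly the same value in everyone analysed. Differences in susceptibility then show in two other places: how long, or how much lipid, it took to reach 50, and whether 50 was reached at all. Neither is a planned outcome, and the people who never reached 50 are outside the analysis set.

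The protocol itself uses the term for the response to the infusion. Section 4.1 speaks of the nausea response that the lipid infusion induces, and section 11.6 of participants who have no such response to it. On that usage, the set for objective 5 is selected on the outcome of objective 5. A null result could then be reported as no link between anxiety or personality and nausea, when the analysis had looked mainly at recovery.

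**Working it through.** **The plan's own figure.** Inputs from section 4.4: difference 25 mm, SD 21.5, two-sided alpha 0.05, power 0.80, 1:1. The two-sample t-test gives 12.65, rounded up to 13 per arm, so 26 in total (power 0.812 at 13 per arm). The 26 reproduces. It was set for the primary comparison; the protocol gives no figure for objective 5.

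**Observable range.** At 5 ml/min, the expected 52 min is 5 × 52 = 260 ml (section 5.2.1 prints 258 ml). The 90-minute limit is 5 × 90 = 450 ml.

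**How many are removed.** Enrolment continues until 26 responders complete. Infused = 26 / response rate, rounded up. The response rates are assumptions.

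| Response rate | 26 / rate | Infused | Non-responders removed |
|---|---|---|---|
| 90% | 28.9 | 29 | 3 |
| 70% | 37.1 | 38 | 12 |
| 60% | 43.3 | 44 | 18 |
| 50% | 52.0 | 52 | 26 |

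**Attenuation from dropping non-responders.** Take time to VAS 50 as normal with mean 52 min, cut at 90 min, and a true trait-time correlation ρ = 0.50. With a = (90 − 52)/SD and λ = φ(a)/Φ(a), the variance ratio after truncation is k = 1 − aλ − λ². The correlation in responders is ρ√k / √(1 − ρ² + ρ²k).

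| Assumed SD (min) | a | Non-response | k | Correlation in responders |
|---|---|---|---|---|
| 6 | 6.33 | about 0 | 1.000 | 0.50 |
| 15 | 2.53 | 0.6% | 0.959 | 0.49 |
| 20 | 1.90 | 2.9% | 0.867 | 0.47 |
| 32 | 1.19 | 11.8% | 0.685 | 0.43 |

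Section 5.2.1 prints 52 ± 6 min without saying what the ± is. If it is an SD, truncation is negligible. SD 32 is an upper illustration and puts about 5% of times below zero. This table concerns a time outcome only; it does not measure the performance of the planned mixed model.

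**What each analysis can detect.** Simulation, 1,500 runs per scenario: log-normal time to VAS 50 (log SD 0.5, assumed), 90-minute cap, enrolment to 26 responders, true correlation 0.5 between trait and susceptibility, and decline after induction generated as unrelated to the trait. Percentage of runs with p < 0.05:

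| Analysis | 90% respond | 70% | 50% |
|---|---|---|---|
| Decline after induction, responders | 5 | 4 | 5 |
| Time to VAS 50, responders only | 63 | 47 | 38 |
| Time to VAS 50, all infused, censored at 90 min | 75 | 83 | 91 |

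The first row follows from the assumption that recovery is unrelated to the trait. It illustrates that a recovery outcome carries no information on susceptibility unless the two are linked; it is not evidence that they are unlinked. For a true correlation of 0.3, the last row falls to 32%, 40% and 49%.

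**Smallest detectable correlation** (80% power, Fisher z): tanh(2.80/√(N − 3)). N = 26 gives 0.53, N = 44 gives 0.41, N = 52 gives 0.38.

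**The case against.** Objective 5 never mentions susceptibility. Relating traits to nausea after induction is a legitimate reading of it, and the mixed model answers that reading. A reader might infer that the objective is unanswerable as planned; the text does not support that.

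Section 10.2 also names no outcome, so nothing bars the during-infusion ratings from the model. Their rate of rise would carry some information on speed of onset among responders. A reader might infer that all variation in induction is discarded; the protocol does not say so, and the exact outcome could be left to an SAP. What an SAP cannot do is bring non-responders back in without contradicting section 10, which fixes the set for all secondary outcomes.

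A reader might also suspect that treatment confounds the trait association. Traits are measured at visit 1, before randomisation, so arm is not a systematic confounder. Adjusting for it is still sensible in 26 people.

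Three further points stand. Participants are told the threshold, the time limit and the drop-out consequence (section 8.3.2), so time to VAS 50 partly reflects reporting behaviour, which may itself depend on traits. Scores of 10 or more on GAD-7 or PHQ-9 are excluded, which narrows the trait range. And the summary describes this relation as exploratory, with no bearing on the primary conclusion.

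**Conclusion.** The concern holds in a limited form. As fixed in sections 5.2.1, 8.5 and 10, objective 5 can describe mainly the course of nausea after induction. It cannot show whether traits relate to who becomes nauseated, or properly how fast, because non-responders are excluded on that outcome and time or volume is not a planned outcome. The titration part does not depend on non-response: the induced score is made similar even if everyone responds. Similar is approximate, since ratings are 5 minutes apart and retching can stop the infusion below 50.

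The size is uncertain because the protocol gives neither a response rate nor a clear SD. On the assumptions shown, between 3 of 29 and 26 of 52 infused participants would be left out, and attenuation of a true 0.50 runs from none to 0.43. The gain from the alternative analysis is clear for a strong association and modest for a weak one. This merits a change to a secondary, exploratory analysis; the primary analysis is unaffected.

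**What to change.** 1. In section 10.2, add an exploratory analysis for objective 5: time from infusion start to VAS 50 or higher (equivalently volume at 5 ml/min) in all participants who start the infusion, both arms pooled since induction precedes stimulation, with non-responders censored at 90 minutes. Use a Cox or similar time-to-event model per questionnaire score, reported with confidence intervals.
2. State how infusion stops for retching, vomiting or participant request are counted in this analysis (section 8.3.2 allows all three).
3. Exempt this analysis from the modified ITT restriction in section 10 and from the dropout handling in sections 5.2.1 and 8.5.
4. Record the during-infusion VAS ratings and the infusion stop time as study data, since the 14 questionnaires in section 8.3.4 do not count them.
5. Keep the mixed model, described as addressing nausea after induction and adjusted for arm.

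Cost: a few lines of text, a small extra analysis and some data capture. Questionnaires already precede the infusion and the ratings are already taken, so no visit or procedure is added. The write-up should say that power for modest associations is low and that participants knew the threshold.

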10.3 Other study parameters

Not applicable.

10.4 Interim analysis

Not applicable.

11. ETHICAL CONSIDERATIONS

11.1 Regulation statement

This study will be conducted according to the most recent version of the Declaration of Helsinki (75th WMA General Assembly, Helsinki, Finland, October 2024), the Medical Research Involving Human Subjects Act (WMO), and adheres to article 82 of the Medical Device Regulation (MDR, EU no 2017/745).

11.2 Recruitment and consent

Healthy volunteers will be recruited through a variety of channels, including advertisements in local and faculty newspapers, flyers/posters in public spaces, social media, and by reaching out to individuals who have previously participated in research and consented to be contacted for future studies, utilizing advertisement document E3_Wervingsmateriaal_Versie2.0_dd 02-04-2025. This document will outline the study's objectives, inclusion criteria and the timeline of this study. The contact details of the coordinating investigator will be provided at the bottom of the advertisement document, including a link/QR-code, that automatically generates an email, for easy access by potential participants. Upon contacting the study team via telephone, volunteers will receive a detailed oral explanation of the study from a researcher, and the written information brochure and informed consent form (see E1-2b_Informatiebrief_en_toestemmingsformulier_Versie2.0_dd 25-03-2025) will be sent via regular mail or email. For volunteers who contact the study team via email, the written information brochure and informed consent form will be promptly provided. Additionally, a verbal explanation of the study will be given over the phone. After sending the written information brochure and providing the verbal explanation, a minimum period of one week is given for the participant to decide whether they would like to participate. The participant is encouraged to contact the investigator by telephone to ask additional questions and to discuss their decision to participate. If the participant does not initiate contact with the researcher within this timeframe, the researcher will reach out to them once, at the earliest 7 days after sending the written information brochure and the verbal explanation, and only if the participant has given permission to do so during the initial conversation or in the initial email. During this contact, the researcher ensures that the participant understands the provided information and addresses any remaining questions. If the participant expresses a positive decision to participate, the first visit will be scheduled at Maastricht University. During this visit, participants will be explicitly asked to state in their own words what the study involves, including the associated risks and burdens. After this, the written informed consent form will be signed, (digital) questionnaires will be answered,

and a second visit for the measurements will be planned. No study procedures will be performed until the informed consent form is signed.

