A duration of 30 minutes was selected based on the mechanism of action of taVNS, which is assumed to act via the activation of the nucleus of the solitary tract (NTS) in the brainstem. Furthermore, this choice is also consistent with other studies on taVNS conducted within our department (NL87188.068.24/METC 24-029). The NTS serves as the primary relay station for vagal input and plays a critical role in modulating autonomic functions. In a previous study by Frangos et al. (24), NTS activity gradually decreased during stimulation but peaked shortly after the cessation of a 7-min stimulation of the cymba conchae. Furthermore, other brain regions exhibited a gradual increase in activity during stimulation, reaching their peak during the post-stimulation phase, with this heightened activity persisting for up to 11 minutes. Hence, a stimulation period of 30 minutes is expected to provide an optimal timeframe for taVNS to exert its maximum effect and to counterbalance the effects of nausea.

Both the taVNS treatment and sham stimulation will be administered using a tVNS device that provides stimulation to the cymba conchae of the left ear. The left side is chosen due to the innervation pattern of the left vagus nerve, which predominantly innervates the stomach and the pyloric area (25, 26). This choice aligns with our ultimate clinical interest in conditions such as gastroparesis and functional dyspepsia. Additionally, it ensures comparability with other studies conducted within our department, including the “tVNS and GI motility” study (NL86446.068.24).

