The stimulation parameters comprise a biphasic rectangular pulse wave with an impulse frequency of 25Hz, impulse duration of 30 seconds, impulse pause of 30 seconds, and pulse width of 450ms. These parameters have been identified as the most optimal treatment frequencies for taVNS based on systematic reviews (27, 28). Active stimulation will be programmed to deliver only subthreshold stimuli. The device will blink when stimulation is delivered. In the sham (control) group, the electrode will be non-conducting, but the device will still blink to maintain blinding (28). The electrodes used in the tVNS and sham groups differ slightly. Consequently, the investigator responsible for programming the devices will be aware of the treatment allocation, while participants will remain blinded. To ensure double blinding, the randomization code will be altered prior to data analysis, ensuring that the investigator conducting the analysis will be blinded to the treatment allocation. The randomization code will be kept confidential until after the modified intention-to-treat analysis has been reported.

During the stimulation phase, nausea severity will be assessed using a 0-100 VAS score, where 0 indicates “no nausea” and 100 represents the “worst nausea imaginable”. VAS scores will be recorded every 5 minutes, continuing for 30 minutes post-stimulation to evaluate the efficacy of taVNS in alleviating nausea. Additionally, other gastrointestinal symptoms and the desire to eat will be measured at predetermined time points using VAS scores.

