4.3 Exclusion criteria

A potential subject who meets any of the following criteria will be excluded from participation in this study:

- Medical history of chronic or severe diseases affecting the cardiovascular, respiratory, urogenital, gastrointestinal/hepatic, haematologic/immunologic, HEENT (head, ears, eyes, nose, throat), dermatological/connective tissue, musculoskeletal, metabolic/nutritional, endocrine, neurological/psychiatric systems.
- A history of major abdominal surgery.
- Gastrointestinal complaints.
- Any use of medication, especially those affecting gastric motility and nausea, apart from oral contraceptives.
- Current or lifetime psychopathology (including PHQ-9 and GAD-7 scores ≥ 10)
- Substance abuse, including excessive alcohol consumption (>20 alcoholic consumptions per week) and the use of recreational drugs.
- Smoking.
- Pregnancy, lactation, or intention to become pregnant during the study period
- Use of devices (e.g., cochlear implants) or other conditions (e.g. wounds, permanent ear-piercing) complicating the use of the tVNS device.

- Administration of investigational drugs or participation in any scientific intervention study that might interfere with this study (to be determined by the principal investigator) within 180 days preceding the commencement of the study.
- Students and employees of Maastricht University are not precluded from participation, unless they have a direct personal, professional or hierarchical position with regards to any of the study team members or their department.

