5.1.2 Sham stimulation

In the control group, sham stimulation will be administered to the same electrode location (left cymba conchae) using an identical device as that used for taVNS. The electrode used for sham stimulation will be non-conducting, ensuring that there is no stimulation of the vagus nerve. Although the devices for tVNS and sham stimulation appear identical, the electrodes for each group are slightly different. Consequently, the investigator responsible for programming the devices will be aware of the treatment allocation. Participants will not be aware of the treatment received since stimulation is provided to the same location, and the device will still blink during both types of stimulation to maintain blinding (28). The randomization code will be altered

before analysis, ensuring that the investigator conducting the data analysis remains unaware of the treatment allocation. The randomization code will be kept confidential until after the modified intention-to-treat analysis has been reported.

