6. INVESTIGATIONAL PRODUCT

In this clinical investigation we will use tVNS R. tVNS L already has a declaration of conformity. However, tVNS R and tVNS L are completely equivalent concerning all electrical as well as mechanical aspects. The only difference is the software of the products. Where in the tVNS L device the stimulation parameters are fixed, these can be changed in the tVNS R for research purposes. See annex

‘D2_Declaration_of_conformity_tVNS_L_signed_Versie1.0_dd 31-05-2021’ and D4_Confirmation_of_equivalence_tVNS_Versie1.0_dd 22-10-2021’. Because the tVNS device will be used outside the intended use of the declaration of conformity this investigation falls under article 82 of the MDR. This exact same device was previously used by our study group in the “RESILIENCE” study (NL84720.068.23/METC23-032).

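### People who have already worn an active auricular vagus nerve stimulator could enrol, which could weaken participant blinding of a self-rated nausea outcome; a stimulation-naive criterion would close the gap cheaply

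*Protocol*

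**What the plan says.** **Recruitment.** Protocol section 11.2 lists newspapers, flyers, posters and social media, and adds recruitment "by reaching out to individuals who have previously participated in research and consented to be contacted for future studies". It does not restrict which earlier studies these people come from. Section 3 says that recruitment follows the procedures of the department's study on taVNS and the acute stress response.

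**Eligibility.** The only limit in section 4.3 on earlier trials concerns investigational drugs or "participation in any scientific intervention study that might interfere with this study (to be determined by the principal investigator) within 180 days" before the start of the study. The only criterion specific to the stimulator is "Use of devices (e.g., cochlear implants) or other conditions (e.g. wounds, permanent ear-piercing) complicating the use of the tVNS device". Previous auricular stimulation is not listed as an exclusion. Nor is it named among the baseline data in sections 8.1.3 and 8.3.4.

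**Earlier studies.** Section 6 states: "This exact same device was previously used by our study group in the “RESILIENCE” study". Section 3 also refers to the acute stress study and to a study of tVNS and gastrointestinal motility, both from the same department.

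**Blinding of participants.** Section 3 states: "In the sham (control) group, the electrode will be non-conducting, but the device will still blink to maintain blinding". Section 5.1.2 gives the reasoning: "Participants will not be aware of the treatment received since stimulation is provided to the same location", together with the blinking light. Sections 3, 5.1.2 and 8.2 acknowledge that the active and sham electrodes differ slightly.

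**Outcome.** Section 8.1.1 makes the primary endpoint a self-rated 0-100 nausea VAS, compared with sham.

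**The concern.** The two features on which section 5.1.2 rests participant blinding are the same ear location and the same blinking light. Both suit a volunteer with nothing to compare them with. They do less for someone who has worn an active electrode and may remember how it looked or how the setting of the current felt. Nothing in section 4.3 keeps such a person out once 180 days have passed, or sooner if the earlier study is judged not to interfere.

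A participant who works out the allocation can bring expectation into the nausea rating. Randomisation does not remove this, because the recognition happens after allocation and differs by arm. With about 13 people per arm, a handful of unblinded participants could shift the contrast. No later analysis can restore blinding that was lost on the test day, so the matter belongs in the eligibility criteria.

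**Working it through.** **1. The plan's own figure.** Section 4.4 uses an unpaired t-test with a difference of 25 mm, SD 21.5, two-sided alpha 0.05 and power 0.80. The standardised difference is 25 / 21.5 = 1.163. The t-test calculation gives 12.65 per arm, rounded up to 13, so 26 in total with power 0.812. The stated 26 reproduces and is not in dispute.

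**2. Can an experienced person enrol?**

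| Step | Protocol section | Result |
|---|---|---|
| Are former research participants approached? | 11.2 | Yes, from unspecified studies |
| Has the group or department run such stimulation studies? | 3, 5.1.1, 6 | Yes; RESILIENCE used the same device |
| Does any criterion exclude previous stimulation? | 4.3 | Only within 180 days, and only if judged to interfere |
| Is previous stimulation among the listed baseline data? | 8.1.3, 8.3.4 | Not named |

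So enrolment of such a person is possible. The protocol does not show how likely it is.

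**3. How could that person recognise the allocation?** Two cues remain.

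- *Setting the current.* Sections 3 and 8.3.2 adjust the current to each participant's sensitivity before nausea induction, and section 5.1.1 describes sensory testing for each participant. The protocol does not say which electrode sham participants wear at this step. If it is the non-conducting one, no sensation can be reached.
- *Appearance.* The electrodes differ slightly, and a previous wearer may notice. The protocol does not say whether participants can see the difference.

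**4. Dependence on intensity.** Sections 3 and 8.3.2 put active stimulation below the sensory threshold. Section 5.1.1 says suprathreshold. Section 13.1, item j, says below the pain threshold. If stimulation is below the sensory threshold, neither arm should feel current during treatment, and recognition depends on the two cues above. If it is suprathreshold, absence of sensation could reveal sham during treatment even to a naive participant, and previous exposure only adds to that.

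**5. Size, under assumptions.** Let *k* of 13 participants in an arm recognise their allocation and each shift the rating by *b* mm. Neither *k* nor *b* is in the protocol.

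- Only sham participants shift: bias = (k / 13) × b.
- Both arms shift, in opposite directions: bias = 2 × (k / 13) × b.

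The type I error is the rejection probability of the two-sided t-test with 13 per arm, SD 21.5, no true effect and a mean difference equal to the bias.

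| k per arm | b (mm) | Who shifts | Bias (mm) | Type I error |
|---|---|---|---|---|
| 1 | 10 | sham only | 1/13 × 10 = 0.8 | 0.051 |
| 3 | 10 | sham only | 3/13 × 10 = 2.3 | 0.058 |
| 3 | 15 | sham only | 3/13 × 15 = 3.5 | 0.068 |
| 4 | 20 | sham only | 4/13 × 20 = 6.2 | 0.108 |
| 2 | 10 | both arms | 2 × 2/13 × 10 = 3.1 | 0.064 |
| 4 | 20 | both arms | 2 × 4/13 × 20 = 12.3 | 0.289 |

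Against the 25 mm design difference, 0.8 mm is 3% and 6.2 mm is 25%. The t-test stands in for the mixed model of section 10.1, and the SD is held at 21.5, so these figures are an order of magnitude only.

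**The case against.** The case on the other side is substantial, and much of it stands.

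- **Exposure is not shown.** A reader might infer that some recruits will have had stimulation and will recognise the sham. The protocol does not support that. Section 11.2 speaks of earlier research in general, as one channel among several. Nothing is said about whom the earlier stimulation studies enrolled, what sham they used, or whether their participants agreed to be contacted again. The strict health criteria in section 4.3 may exclude some of them. The text supports *could*, not *will*.
- **The 180-day rule is broader than drug carry-over.** It might be read as a pharmacological washout, but it covers any interfering intervention study and can therefore reach stimulation studies. Its limits are the time window and the discretion it leaves to the principal investigator.
- **Subthreshold stimulation weakens the mechanism.** On the reading in sections 3 and 8.3.2, a lack of sensation during treatment does not identify sham. The threshold-finding step and the electrode difference remain, but how sham is handled at that step is not described. A naive participant might also notice a lack of sensation there.
- **Direction is not fixed.** A reader might assume that bias must favour taVNS. Someone who previously had sham, or active stimulation without benefit, may expect nothing. Bias towards the hypothesis is plausible but not certain.

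These points limit the size of the concern. They do not remove the gap in section 4.3: a person with direct experience of an active device can be eligible.

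**Conclusion.** The gap is real and modest. Sections 11.2 and 4.3 together allow someone with previous active auricular stimulation into a sham-controlled trial with a self-rated primary outcome, and the participant-blinding measures in section 5.1.2 were not built for that person. Whether anyone of this kind will enrol, and what it would do to the ratings, cannot be read from the protocol.

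Under the assumed values, one or two people with modest shifts make a negligible difference. The effect becomes material only if several per arm recognise their allocation and shift their ratings markedly. The point is therefore a cheap improvement to the design. It is not evidence that the comparison will be biased. How much weight it deserves depends on which statement of stimulation intensity applies, and that is unresolved in the protocol.

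**What to change.** Add to section 4.3 an exclusion for any previous auricular vagus nerve stimulation, active or sham, at any time, and check it with one question at visit 1. The 180-day rule can stay as it is for other intervention studies. Once the criterion is in place, restricting the re-contact channel in section 11.2 adds little.

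The cost is one line, one question and a slightly smaller recruitment pool. The other recruitment channels and the target of 26 are unaffected. If the sponsor prefers not to lose volunteers, the minimum is to record previous exposure and ask each participant to guess the allocation after stimulation. That would show whether the problem occurred but would not prevent it.

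Separately, reconcile the statements on stimulation intensity in sections 3 and 8.3.2 with those in sections 5.1.1 and 13.1, and state how the current-setting step is carried out in the sham arm. The exclusion would not deal with any unblinding of naive participants that follows from the intensity chosen.
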